## **9.10 Packaging and Labeling**

The specifications and storage conditions of brentuximab vedotin are provided in [Table 9.b](#).

Brentuximab vedotin vials will be packaged as single-use cartons. Each carton will contain 1 vial of the investigational product, and the vial and carton will be labeled to meet the requirements of the China Food and Drug Administration.

**Table 9.b      Investigational Product**

Investigational product	Brentuximab vedotin
Content	50 mg/vial
Concentration	5 mg/mL (after reconstitution)
Container	Clear, colorless, glass vial
Packing unit	1 vial/carton
Property	Sterile white to off-white lyophilized cake or powder. Reconstituted products are clear or slightly opaque.
Protection from light	Reconstituted products should be protected from light until preparation.
Storage	Refrigeration (2°C-8°C)
Manufacturer and country	CCl [REDACTED]

### **9.11 Storage, Handling, and Accountability**

Vials containing study treatment must be refrigerated at 2°C to 8°C in a secure location (eg, locked room) accessible only to the pharmacist, the investigator, or a duly designated person.

Study treatment does not contain preservatives; therefore, opened and reconstituted vials of study treatment must be used within 24 hours when stored under refrigeration at 2°C to 8°C.

Reconstituted study treatment should not be stored at room temperature. It is recommended that study treatment vials and solutions be protected from direct sunlight until the time of use. Reconstituted vials must not be shaken.

Drug accountability instructions are provided in the Pharmacy Manual.

## **10.0 STUDY CONDUCT**

This trial will be conducted in compliance with the protocol, Good Clinical Practice (GCP), applicable regulatory requirements, and International Conference on Harmonisation (ICH) guidelines.

### **10.1 Study Personnel and Organizations**

The contact information for the clinical laboratories, the coordinating investigator, the interactive web response system (IWRS) provider, and the contract research organization (CRO) is presented in the attachment. A full list of investigators is available in the sponsor's investigator database.

### **10.2 Arrangements for Recruitment of Patients**

Recruitment and enrollment strategies for this study may include recruitment from the investigator's local practice or referrals from other physicians. If advertisements become part of the recruitment strategy, they will be reviewed by the institutional review board (IRB)/ independent ethics committee (IEC).

### **10.3 Study Procedures**

Refer to the Schedule of Events ([Appendix A](#)) for the study procedures. Additional details are provided as necessary in the sections that follow.

#### **10.3.1 Informed Consent**

Each patient must provide written informed consent before any study-required procedures are conducted, unless those procedures are performed as part of the patient's standard care. All the results of examinations (eg, HIV, HBV, HCV), imaging studies (eg, CT or MRI), tumor histology (CD30+ HL or sALCL, and ALK status for patients with sALCL), and bone marrow examination that were performed as part of routine care before informed consent has been signed may be used as screening data if the informed consent is obtained from the patient and the tests are performed within 28 days (14 days for bone marrow examination) before the first dose.

#### **10.3.2 Enrollment**

The investigator or investigator's designee will access the IWRS at the screening visit to obtain a unique subject identification number. A subject is considered to be eligible to enter the enrollment visit when the eligibility criteria are met. The subject identification numbers will be used consistently throughout the entire study and must not be changed.

Subjects who do not meet eligibility criteria within the screening period will not be eligible for enrollment. However, subjects may be rescreened at the discretion of the investigator/ subinvestigator, provided that the subject has not been registered as a screen failure. If a subject is being rescreened, the investigator/subinvestigator must obtain additional written informed consent to reconfirm the subject's consent to participate in this study. Subjects may be rescreened only

once. Subjects who will not be rescreened or are determined not eligible after rescreening must be considered screen failures.

The first dose of brentuximab vedotin should be started within 7 days after enrollment. If the first dose cannot be started within 7 days, screening can be repeated after reconsenting.

### **10.3.3 Patient Demographics**

The date of birth, race, ethnicity, and sex of the patient are to be recorded during the screening period (Days -28 to 0).

### **10.3.4 Medical History**

During the screening period (Days -28 to 0), a complete medical history will be compiled for each patient. The history will emphasize the background and progress of the patient's malignancy and include a description of prior therapies for it. In addition, concomitant medications and procedures will be recorded as specified in Section [10.3.12](#).

Medical history will be evaluated for the following categories of clinically significant diseases or procedures that have been resolved or completed by the day before the first dose of brentuximab vedotin:

1. Any diseases that meet the exclusion criteria (including all that were resolved before enrollment).
2. Any diseases or procedures within the past 3 months that do not fall within category 1, except transient diseases (eg, upper respiratory inflammation, common cold, headache, diarrhea).
3. Any other diseases that are considered to possibly affect the evaluation of drug efficacy.

Complications will also be evaluated for any symptoms or diseases that are present at the first dose of brentuximab vedotin. Complications include clinically relevant abnormalities in laboratory tests, 12-lead ECGs, or physical findings. Details of complications (diagnostic results, whenever possible) should be given.

### **10.3.5 ECOG Performance Status**

ECOG performance status (see [Appendix D](#)) will be measured during the screening and treatment periods. The timing of assessments will be as follows:

- Screening period: Days -28 to 0.
- Cycles 1 and 2: Days 1, 8, and 15; to be performed before study treatment on Day 1.
- Cycle 3 and subsequent cycles: Days 1 and 15; to be performed before study treatment on Day 1.
- Safety follow-up period: on the 30th day ( $\pm 7$  days) after the last dose of brentuximab vedotin.

### **10.3.6 Patient Height**

Height will be measured only during screening (within 28 days before the first dose of study drug).

### **10.3.7 Weight**

Weight will be measured during the screening and treatment periods. The timing of assessments will be as follows:

- Screening period: Days -28 to 0.
- Cycle 1: Day 1 within 3 days before study treatment.
- Cycle 2 and subsequent cycles: Day 1 of each cycle within 1 day before study treatment.
- Safety follow-up period: on the 30th day ( $\pm 7$  days) after the last dose of brentuximab vedotin.

### **10.3.8 Vital Signs**

Vital sign measurements include blood pressure in the sitting position, pulse rate, and axillary temperature. The timing of assessments will be as follows:

- Screening period: Days -28 to 0.
- Cycles 1 and 2: Days 1, 8, and 15; to be measured on Day 1 of Cycles 1 and 2 at predose, 15 minutes ( $\pm 5$  minutes) and 30 minutes ( $\pm 5$  minutes) after the start of study drug infusion and at the end of dosing ( $\pm 10$  minutes).
- Cycle 3 and subsequent cycles: Days 1 and 15; to be measured on Day 1 of Cycle 3 and subsequent cycles at predose and at the end of dosing (-5 minutes to +10 minutes).
- Safety follow-up period: on the 30th day ( $\pm 7$  days) after the last dose of brentuximab vedotin.

### **10.3.9 ECGs**

A 12-lead ECG will be administered as follows:

- Screening period: Days -14 to 0; the screening ECG within 3 days of study dose on Day 1 of Cycle 1 may be substituted for the ECG on Day 1 of Cycle 1.
- Cycle 1: Day 1 within 3 days before study treatment and after completion of the infusion (+2 hour).
- Cycle 2 and subsequent cycles: Day 1 of each cycle within 1 day before study treatment.
- Safety follow-up period: on the 30th day ( $\pm 7$  days) after the last dose of brentuximab vedotin.

### **10.3.10 Clinical Laboratory Evaluations**

Clinical laboratory evaluations will be performed locally. Clinical laboratory evaluations will be performed as outlined in this section.

#### **10.3.10.1 Clinical Chemistry, Hematology, and Urinalysis**

Blood samples for analysis of the clinical chemistry and hematological parameters and urine samples for analysis of the parameters shown in [Table 10.a](#) will be collected. The timing of the assessments will be as follows:

##### **Hematology**

- Screening period: Days -14 to 0; screening testing within 3 days of study dose on Day 1 of Cycle 1 may be substituted for testing on Day 1 of Cycle 1.
- Cycles 1 and 2: Days 1, 2, 4, 8, and 15; the testing on Day 1 of Cycle 1 is to be performed within 3 days before study treatment and the testing on Day 1 of Cycle 2 is to be performed within 1 day before study treatment.
- Cycle 3 and subsequent cycles: Days 1 and 15; the testing on Day 1 of each cycle is to be performed within 1 day before study treatment on Day 1.
- Safety follow-up period: on the 30th day ( $\pm 7$  days) after the last dose of brentuximab vedotin.

##### **Chemistry A**

- Screening period: Days -14 to 0; screening testing within 3 days of study dose on Day 1 of Cycle 1 may be substituted for testing on Day 1 of Cycle 1.
- Cycles 1 and 2: Days 1, 8, and 15; the testing on Day 1 of each cycle is to be performed within 3 days before study treatment and the testing on Day 1 of Cycle 2 is to be performed within 1 day before study treatment.
- Cycle 3 and subsequent cycles: Days 1 and 15; the testing on Day 1 of each cycle is to be performed within 1 day before study treatment.
- Safety follow-up period: on the 30th day ( $\pm 7$  days) after the last dose of brentuximab vedotin.

Samples of glucose must be taken under fasting conditions (at least 4 hours after a meal) at screening and on Day 1 of Cycle 1. At other time points, although fasting levels (at least 4 hours after a meal) should be measured as a rule, nonfasting levels are also permitted; if a nonfasting level is measured, meal times must be recorded on the source document.

##### **Chemistry B**

- Screening period: Days -14 to 0.
- Safety follow-up period: on the 30th day ( $\pm 7$  days) after the last dose of brentuximab vedotin.

Samples of total cholesterol and triglycerides must be taken under fasting conditions (at least 4 hours after a meal) at screening. At other time points, although fasting levels (at least 4 hours after a meal) should be measured as a rule, nonfasting levels are also permitted; if a nonfasting level is measured, meal times must be recorded on the source document.

### **Coagulation**

- Screening period: Days -14 to 0; screening testing within 3 days of study dose on Day 1 of Cycle 1 may be substituted for testing on Day 1 of Cycle 1.
- Cycle 1: Days 1 and 15; the testing on Day 1 to be performed within 3 days before study treatment.
- Cycle 2 and subsequent cycles: Day 1 of each cycle; to be performed within 1 day before study treatment.
- Safety follow-up period: on the 30th day ( $\pm 7$  days) after the last dose of brentuximab vedotin.

### **Viral test**

- Screening period: Day -28 to 0.

For patients who are HBV core antibody positive/HBV surface antigen negative/HBV surface antibody negative at screening, it is recommended to follow-up for HBV-DNA levels per local practice.

### **Urinalysis**

- Screening period: Day -14 to 0.
- Cycle 2 and subsequent cycles: Day 1 of each cycle; to be performed within 1 day before study treatment.
- Safety follow-up period: on the 30th day ( $\pm 7$  days) after the last dose of brentuximab vedotin.

**Table 10.a Clinical Laboratory Evaluations**

Tests	Panels
Hematology	Red blood cells, hemoglobin content, hematocrit, white blood cells, platelets, differential white blood cells (neutrophils, eosinophils, basophils, lymphocytes, monocytes), reticulocyte
Chemistry A (a)	Sodium, potassium, chloride, albumin, calcium, phosphorus, glucose, BUN, uric acid, creatinine, total bilirubin, AST, ALT, ALP, LDH, GGT
Chemistry B (b)	HbA1c, total cholesterol, triglycerides, TSH, FT3, FT4
Coagulation test	INR, PT, APTT
Viral test	HIV antibody, HBV surface antigen, HBV surface antibody, HBV core antibody, HBV DNA if appropriate, HCV antibody
Urinalysis	pH, protein, glucose, ketones, blood, urobilinogen

ALP=alkaline phosphatase, ALT=alanine aminotransferase, APTT=activated partial thromboplastin time, AST=aspartate aminotransferase, BUN=blood urea nitrogen, FT3=free triiodothyronine, FT4=free thyroxine, GGT=gamma-glutamyl transpeptidase, HbA1c=hemoglobin A1c, HBV=hepatitis B virus, HCV=hepatitis C virus, HIV=human immunodeficiency virus, INR=international normalized ratio, LDH=lactate dehydrogenase, PT=prothrombin time, TSH=thyroid-stimulating hormone.

(a) Samples for glucose must be taken under fasting conditions (at least 4 hours after a meal) at screening and on Day 1 of Cycle 1. At other time points, although fasting levels (at least 4 hours after a meal) should be measured as a rule, nonfasting level are also permitted; if a nonfasting level is measured, meal times must be recorded on the source document.

(b) Samples for total cholesterol and triglycerides must be taken under fasting conditions (at least 4 hours after a meal) at screening. At other time points, although fasting levels (at least 4 hours after a meal) should be measured as a rule, nonfasting levels are also permitted; if a nonfasting level is measured, meal times must be recorded on the source document.

### **10.3.11 Pregnancy Test**

A serum pregnancy test will be performed for women of childbearing potential at screening within 2 weeks before the first dose of brentuximab vedotin. The results from this test must be available and negative before the first dose of brentuximab vedotin is administered. Timing of assessments will be as follows:

- Screening period: Days -14 to 0.
- Safety follow-up period: on the 30th day ( $\pm 7$  days) after the last dose of brentuximab vedotin.

### **10.3.12 Concomitant Medications and Procedures**

Medications used by the patient and therapeutic procedures completed by the patient will be recorded in the eCRF from the first dose of study medication through the safety follow-up visit. During outpatient treatment, the use of medications other than brentuximab vedotin and/or medical procedures will be elicited every visit. See Section 9.3 and Section 9.4 for a list of medications and therapies that are prohibited and/or allowed, respectively, during the study.

### **10.3.13 AEs**

Monitoring of AEs, serious and nonserious, will be conducted throughout the study. Changes in severity of peripheral neuropathy should be monitored in detail.

Refer to Section [11.0](#) for details regarding definitions, documentation, and reporting of pretreatment events (PTEs), AEs, and SAEs.

### **10.3.14 Disease Assessment**

Tumor response will be evaluated according to the Revised Response Criteria for Malignant Lymphoma [\[1\]](#).

All imaging will be performed with contrast, except for subjects in whom contrast imaging is difficult because of hypersensitivity to contrast medium, bronchial asthma, renal impairment, or other conditions.

Measurable lesions are those that meet all the following criteria:

- Lymph nodes diagnosed as lymphoma lesions, or nodular masses involving extranodal organs on CT imaging.
- Lesions that can be accurately measured in 2 perpendicular directions on CT cross-sectional images.
- Lesions with longest diameter  $\geq 1.5$  cm on CT cross-sectional images.
- FDG-PET positive lesions.

As many as 6 target lesions will be selected among the measurable lesions, whether nodal or extranodal, in order of decreasing longest diameter on CT cross-sectional images.

B symptoms will be assessed at prespecified time points as described in the Schedule of Events ([Appendix A](#)).

Bone marrow aspirate or biopsy will be performed within 2 weeks before the first dose of brentuximab vedotin (it is not necessary to repeat these procedures in patients with a positive bone marrow aspirate or biopsy performed after the most recent antineoplastic therapy). For patients with bone marrow involvement at Baseline, bone marrow aspirate or biopsy is required to confirm the CR status. Bone marrow aspirate or biopsy samples will be collected within 2 weeks after CT scans. Further bone marrow assessments are not required after bone marrow aspirate or biopsy becomes negative.

Timing of CT scans will be as follows:

- Screening period: Days -28 to 0.
- Cycles 2, 4, 7, 10, 13, and 16: Days 15 through 21 (before study treatment in the next cycle).

Subjects who discontinue study treatment or assessments for the reasons stated in Section 10.6 other than progressive disease (PD) and have not undergone assessment within the past 6 weeks should have tumor response assessed during the safety follow-up whenever possible.

Subjects who discontinue study treatment for any reason other than PD will have CT scans every 12 weeks ( $\pm$ 14 days) for the first 12 months and at 18 months after EOT until disease progression, death, withdrawal of consent, or initiation of a new treatment, whichever occurs first.

Subjects with symptoms suggestive of PD should be evaluated radiographically to assess disease status at the time the symptoms occur whenever possible.

PET scans will be performed at baseline and on Days 15 through 21 of Cycles 4 and 7 (before study treatment of next cycle). No additional PET scanning is required beyond Cycle 7 unless clinically indicated.

Refer to the study manual for the details of CT/PET scans for the assessment of antitumor effect.

#### **10.3.15 PK Measurements**

Blood samples for PK (ADC and total antibody [TAb] in serum, MMAE in plasma) will be taken at prespecified time points as described in Table B ([Appendix A](#)).

Refer to Sample Management Plan and Laboratory Manual for PK sample collection, processing, storage condition, and shipment.

#### **10.3.16 Immunogenicity Measurements**

Blood samples for immunogenicity (in serum) assessments will be taken at prespecified time points as described in Table B ([Appendix A](#)). On dosing days, the blood samples for immunogenicity assessments must be collected before dosing.

Detailed information about the immunogenicity blood volume, blood sample collection, processing, storage conditions, and shipment will be provided in the Sample Management Plan and Laboratory Manual.

Positive ATA screening samples will be further tested for true positivity. Confirmed true positive ATA samples will be further characterized for neutralizing activity.

### **10.4 Completion of Treatment**

Patients will be considered to have completed study treatment if they complete 16 cycles of treatment with brentuximab vedotin or if they experience PD. Patients who discontinue study treatment for any reason other than withdrawal of consent will have safety follow-up assessments through 30 days ( $\pm$ 7 days) after receiving their last dose of brentuximab vedotin.

### **10.5 Completion of Study**

Patients will be considered to have completed the study if they complete 16 cycles of treatment with brentuximab vedotin and have completed the 18-month follow-up or have died.

## **10.6 Discontinuation of Treatment With Study Drug and Patient Replacement**

Treatment with study drug may be discontinued for any of the following reasons:

- AE.
- Protocol violation.
- PD.
- Study terminated by sponsor.
- Withdrawal by subject.
- Lost to follow-up.
- Administrative decision by the investigator/subinvestigator or the sponsor.
- Pregnancy.
- Completed 16 cycles of treatment at response (CR or PR) or SD.
- Initiation of subsequent stem cell transplant
- Other.

Once study drug has been discontinued, all study procedures outlined for the safety follow-up visit will be completed as specified in the Schedule of Events ([Appendix A](#)). The primary reason for study drug discontinuation will be recorded on the eCRF.

Reasons that may cause a subject to be replaced include but are not limited to:

- Patient does not meet Inclusion Criterion 2.
- Patient has not taken at least 1 dose of brentuximab vedotin.
- Patient is not response evaluable according to the Revised Response Criteria for Malignant Lymphoma [1].

## **10.7 Withdrawal of Patients From Study**

A patient may be withdrawn from the study for any of the following reasons:

- Lost to follow-up.
- Study terminated by sponsor.
- Withdrawal by subject.
- Other.

The consequence of study withdrawal is that no new information will be collected from the withdrawn patient and added to the existing data or any database.

The sponsor or designee must be notified in writing if a patient is withdrawn from study treatment or from the study. The reason(s) for withdrawal must be documented in the patient's medical records. The investigators should make every reasonable effort to keep each patient on the study until all planned treatments and assessments have been performed. If a patient withdraws from study treatment, every attempt should be made to follow the patient until death or study closure. Final treatment assessments should be performed before any other therapeutic intervention when possible. Additionally, any planned alternative treatments should be documented in the patient's medical records and eCRF.

## **10.8 Study Compliance**

Study drug will be administered or dispensed only to eligible patients under the supervision of the investigator or identified subinvestigator(s). The appropriate study personnel will maintain records of study drug receipt and dispensing.

## **10.9 Long-term Follow-up Assessments**

Patients who discontinue study treatment with SD or better will be followed for PFS until disease progression, death, withdrawal of consent, or initiation of a new treatment, whichever occurs first. A CT scan will be performed every 12 weeks ( $\pm 14$  days) for the first 12 months and at 18 months after the EOT. Patients will be followed for OS every 12 weeks ( $\pm 14$  days) until death, withdrawal of consent, or study closure, whichever occurs first. Survival information may be collected by methods including, but not limited to, telephone, e-mail, or mail. Patients will be followed until all patients have had the opportunity to be followed for 18 months after EOT. The study will be closed when all patients enrolled have completed the required follow-up.

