## **7.0 STUDY DESIGN**

### **7.1 Overview of Study Design**

This is a single-arm, open-label, multicenter, phase 2 study designed to evaluate the efficacy, safety, and PK of brentuximab vedotin as a single agent in Chinese patients with relapsed/refractory CD30+ HL or sALCL. Brentuximab vedotin will be administered as a single, 1.8 mg/kg IV infusion on Day 1 of each 3-week cycle.

Patients will receive a maximum of 16 cycles if they do not meet the criteria for removal from the study. Patients will be assessed for overall response using the Revised Response Criteria for Malignant Lymphoma [1]. Dedicated computed tomography (CT) scans (neck, chest, abdomen, and pelvis) will be performed at Baseline and at Cycles 2, 4, 7, 10, 13, and 16, and positron emission tomography (PET) scans will be performed at Baseline and at Cycles 4 and 7. No additional PET scanning is required beyond Cycle 7 unless clinically indicated. B symptoms will be assessed at Baseline and on Day 1 of each cycle.

Patients may continue on study treatment until the sooner of disease progression, unacceptable toxicity, or completion of 16 cycles. Patients, including those who discontinue study treatment for any reason other than withdrawal of consent, will have safety follow-up assessments through 30 days after the last dose of study drug (end of treatment [EOT]). Patients who discontinue study treatment with stable disease (SD) or better will be followed for PFS until disease progression, death, withdrawal of consent, or initiation of a new treatment, whichever occurs first. A CT scan will be performed every 12 weeks for the first 12 months and at 18 months after EOT. Patients will be followed for OS every 12 weeks until death, withdrawal of consent, or study closure, whichever occurs first. All patients will have the opportunity to be followed for 18 months after EOT. The study will be closed when all patients enrolled have completed the required follow-up.

Toxicity will be evaluated according to the National Cancer Institute Common Terminology Criteria for Adverse Events (NCI CTCAE), version 4.03, effective 14 June 2010 [2]. Laboratory values, vital signs, and electrocardiograms (ECGs) will be obtained to evaluate the safety and tolerability of brentuximab vedotin. Serial blood samples for determination of the serum/plasma concentration and immunogenicity of brentuximab vedotin will be obtained at prespecified time points as described in Table B in [Appendix A](#).

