### **7.3 Duration of Study**

The screening period will be up to 4 weeks, and the treatment period will be up to 16 cycles (approximately 12 months). Patients will have safety follow-up assessments through 30 days after the last dose of brentuximab vedotin. All patients who discontinue brentuximab vedotin for any

reason other than withdrawal of full consent will undergo a long-term follow-up every 12 weeks after the safety follow-up assessments. Patients will be followed until all patients have had the opportunity to be followed for 18 months after EOT. The study will be closed when all patients enrolled have completed the required follow-up. It is expected that the study will last approximately 3.5 years.

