(e) Samples of glucose must be taken under fasting conditions (at least 4 hours after a meal) at screening and on Day 1 of Cycle 1. At other time points, although fasting levels (at least 4 hours after a meal) should be measured as a rule, nonfasting levels are also permitted; if a nonfasting level is measured, the meal times must be recorded on the source document.

(f) Samples of total cholesterol and triglycerides must be taken under fasting conditions (at least 4 hours after a meal) at screening. At other time points, although fasting levels (at least 4 hours after a meal) should be measured as a rule, nonfasting levels are also permitted; if a nonfasting level is measured, the meal times must be recorded on the source document.

(g) See Table B for details regarding PK and immunogenicity draws and windows. Immunogenicity samples must be taken before dosing.

(h) In patients with a positive bone marrow aspirate or biopsy following the most recent treatment of malignant tumor, bone marrow aspirate or biopsy do not need to be repeated.

(i) ECG on Day 1 of Cycle 1 within 3 days before study treatment and after completion of the infusion (+2 hours).

(j) On Days 15-21 after study drug dose of each cycle and before study drug dose of the next cycle.

(k) Sampling for PK and immunogenicity will be taken every 2 cycles after Cycle 3.

(l) CT scan will be performed every 3 cycles after Cycle 4 (Cycles 4, 7, 10, 13 and 16). It does not need to be performed at Cycle 3.

(m) PET scan will be performed at Cycles 4 and 7. No additional PET scanning is required beyond Cycle 7 unless clinically indicated.

(n) For patients with bone marrow involvement at Baseline, bone marrow aspirate or biopsy is required to confirm the CR status. Bone marrow aspirate or biopsy samples will be collected within 2 weeks after CT scans. Further bone marrow assessments are not required after bone marrow aspirate or biopsy becomes negative.

- (o) Safety follow-up assessments should be performed before initiation of subsequent antineoplastic therapy.
- (p) If possible, CT scans and B symptom assessments should be performed if not done within the previous 6 weeks.
- (q) Patients who discontinue study treatment with SD or better will be followed for PFS until disease progression, death, withdrawal of consent, or initiation of a new treatment, whichever occurs first. A CT scan will be performed every 12 weeks ( $\pm 14$  days) for the first 12 months and at 18 months after EOT.

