### 7.8.2 Secondary Efficacy Endpoint(s)

CR rate per investigator will be summarized with 2-sided 95% exact confidence intervals using the safety/mITT population. A sensitivity analysis of CR rate per investigator will also be summarized using the Per-protocol population

DOR and PFS will be estimated base on the investigator assessments using PET scans, CT scans, as well as clinical evaluations according to the IWG revised response criteria. DOR will primarily be summarized using the subset of patients with a CR or PR in the safety/mITT population; a sensitivity analysis of DOR will also be summarized using the subset of patients with a CR or PR in the Per-protocol population. PFS and OS will be summarized using the safety/mITT population.

DOR in subjects with a CR or PR is defined as the time from start of the first documentation of objective tumor response (CR or PR) to the first subsequent documentation of objective tumor progression or to death due to any cause, whichever comes first. DOR will be censored on the day of the last assessment of measured lesions documenting absence of PD for patients who do not have objective tumor progression and are still on study at the time of analysis, are given antitumor treatment other than the study treatment or SCT, or are removed from study prior to documentation of objective tumor progression.

PFS is defined as the time from the first dose until disease progression or death due to any cause, whichever occurs first. PFS will be censored on the day of the last assessment of measured lesions documenting absence of PD for patients who do not have objective tumor progression and are still on study at the time of analysis, are given antitumor treatment other than the study treatment or SCT, or are removed from study prior to documentation of objective tumor progression. Patients lacking an evaluation of tumor response after their first dose will have their event time censored at the day of first dose.

OS is defined as the time from the first dose until death due to any cause. In the absence of confirmation of death, survival time will be censored at the last date the patient is known to be alive. Patients lacking data beyond the day of first dose will have their survival time censored at the day of first dose.

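### Two entry rules for post-treatment CT diverge for patients who stop without PD and without a response category, so their PFS follow-up is undefined

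*Protocol*

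**What the plan says.** Protocol 10.3.14 sets the imaging rule: "Subjects who discontinue study treatment for any reason other than PD will have CT scans every 12 weeks" during the first 12 months, with another at 18 months after EOT. It dates on-treatment CT as "Cycles 2, 4, 7, 10, 13, and 16: Days 15 through 21". Patients who stop without PD and have had no assessment in the preceding 6 weeks "should have tumor response assessed during the safety follow-up whenever possible"; Table A footnote (p) repeats that request.

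Other places set a different entry condition, each followed by the same 12-weekly and 18-month CT schedule:

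- Protocol 10.9: "Patients who discontinue study treatment with SD or better will be followed for PFS until disease progression".
- Protocol 7.1: "Patients who discontinue study treatment with stable disease (SD) or better will be followed for PFS".
- Appendix A, Table A footnote (q): "Patients who discontinue study treatment with SD or better will be followed for PFS until disease progression, death".
- The Study Summary (2.0) and SAP 4.4 carry the same condition.

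Protocol 7.3 is wider again but does not mention scans: patients who stop for any "reason other than withdrawal of full consent will undergo a long-term follow-up every 12 weeks".

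SAP 7.8.2 counts progression or death from any cause as the PFS event. It adds: "Patients lacking an evaluation of tumor response after their first dose will have their event time censored at the day of first dose".

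**The concern.** A patient who stops for toxicity after one or two doses may never have been given a response category. Under 10.3.14 that patient has CT every 12 weeks. Under 10.9 and footnote (q), which belongs to the schedule that sites work from, the patient does not qualify. Two sites could handle identical patients differently and both be following the protocol.

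What is at stake is PFS. If no post-dose evaluation is ever made, the patient is censored at time zero. Patients who stop early for toxicity may differ in prognosis from those still being scanned, so this censoring may not be independent of outcome. The cohorts are small enough for a few such patients to matter.

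**Working it through.** **1. The plan's own figures.** Protocol 14.3 gives the chance of at least 9 responses in 22 HL patients at a true ORR of 65%, and of at least 5 in 8 sALCL patients at 80%. Exact binomial tails give 0.9942 and 0.9437, matching the stated >99% and >94%. Neither depends on long-term scans, because Protocol 14.1.3 counts ORR by EOT.

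**2. Who is treated differently.** Take patients who stop without PD:

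| Status at stopping | 10.3.14 | SD-or-better wording | PFS under SAP 7.8.2 if no later scan is done |
|---|---|---|---|
| CR, PR or SD | scanned | scanned | censored at last assessment without PD |
| Earlier evaluable scan, last scan not evaluable | scanned | unclear | censored at last assessment without PD |
| No post-dose evaluation | scanned | no scheduled scan | censored at day of first dose |

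The clear conflict, and the loss of all PFS time, are in the last row.

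**3. When a patient can be in the last row.** With no dosing delay, Cycle 2 begins on study day 22. Days 15 to 21 of that cycle are study days 21 + 15 = 36 to 21 + 21 = 42. A patient who stops before then has no scheduled post-baseline CT behind them.

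**4. Whether the safety follow-up closes the gap.** After a single dose the visit falls on day 1 + 30 = 31, window 24 to 38. The assessment is requested only where possible and only if none was done in the previous 6 weeks (42 days). Using SAP day numbering, which has no day 0, a baseline CT on day -11 is 31 + 11 - 1 = 41 days before day 31, and one on day -14 is 31 + 14 - 1 = 44 days before. On a literal reading of footnote (p), the first baseline scan would meet the 6-week condition and no post-dose scan would be asked for. That is one possible reading, and the point does not depend on it. The safeguard reduces the group but does not empty it.

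**5. Weight of one patient.** HL: 1/22 = 4.5%. sALCL: 1/8 = 12.5%. These are shares of the planned cohorts.

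**6. How many.** The documents give no rate of stopping before a response category. Assuming a rate q between 2% and 15%, the chance of at least one such patient among n is 1 - (1 - q)^n:

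- HL, n = 22: 1 - 0.98^22 = 0.359 to 1 - 0.85^22 = 0.972.
- sALCL, n = 8: 1 - 0.98^8 = 0.149 to 1 - 0.85^8 = 0.728.
- All, n = 30: 1 - 0.98^30 = 0.4545 to 1 - 0.85^30 = 0.992. The expected number is 30 × 0.02 = 0.6 to 30 × 0.15 = 4.5.

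The range is illustrative. It also overstates the final number, because some of these patients would get a category at safety follow-up.

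**7. Deaths.** OS follow-up is not limited by response category, so deaths are still collected. SAP 7.8.2 does not say whether a death in a patient with no post-dose evaluation counts as a PFS event or yields to day-of-first-dose censoring.

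**The case against.** The best defence is that this is loose drafting with built-in protection. None of the five places says that other patients are not to be scanned. Protocol 10.3 presents the sections after the schedule as supplying further detail, so 10.3.14 can be read as the fuller rule. The safety follow-up assessment is aimed at this very patient, and a result of SD or better then satisfies both wordings. Tumor follow-up ends at a new treatment under either rule, so the PFS time that alignment would recover is unknown. Informative censoring is plausible but not demonstrated.

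Much of this stands. It limits the consequence to a residual group and makes the loss possible rather than certain. It does not settle which rule a site should follow: 10.9 and footnote (q) are operative text, and the safeguard is best effort only.

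Some stronger inferences are not supported:

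- *Progression is never looked for in these patients.* Section 10.3.14 asks for imaging, where possible, when symptoms suggest PD, whatever the response category.
- *Each such patient removes 1/22 or 1/8 of the PFS sample.* Censored patients remain in the safety/mITT set. Section 10.6 also allows a patient who is not response evaluable to be replaced.
- *A last scan that cannot be evaluated also sends PFS back to the first dose.* A patient with an earlier evaluable scan keeps PFS time up to the last assessment without PD.

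**Conclusion.** The contradiction is real and should be resolved. It concerns patients who stop without PD and without a response category, mainly before study days 36 to 42 and without a safety follow-up assessment. Those with no post-dose evaluation stay in the analysis set but contribute no PFS time, and the censoring may be informative. One such patient is about 4.5% of the planned HL cohort or 12.5% of the planned sALCL cohort. How many will occur cannot be taken from the documents, and the 2% to 15% range above is an assumption.

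The reach is limited. PFS is secondary and descriptive. ORR is counted by EOT, DOR uses responders only, OS follow-up is unrestricted by response, and the design probabilities do not change. A reader might infer a threat to the primary result; there is none.

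**What to change.** Reconcile the text to the rule in Protocol 10.3.14. In Protocol 2.0, 7.1 and 10.9, Table A footnote (q) and SAP 4.4, replace the SD-or-better condition with: *for a reason other than PD, including patients with no post-baseline response assessment*. Leave the clause that ends follow-up in each place as it stands.

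In SAP 7.8.2, add that a death in a patient with no post-dose tumor evaluation counts as a PFS event on the date of death, in line with the PFS definition there, and that day-of-first-dose censoring applies only to such patients not known to have died.

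The cost is one protocol wording amendment and matching SAP edits. It adds no scans beyond those that 10.3.14 already requires and does not change the sample size.
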